## APPENDIX 3. RESPONSE CRITERIA FOR CNS METASTASES PROPOSED BY RANO-BM

	Complete Response	Partial response	Stable disease	Progressive disease
Target lesions	None	≥30% decrease in sum longest distance relative to baseline	<30% decrease relative to baseline but <20% increase in sum longest distance relative to nadir	≥20% increase in sum longest distance relative to nadir*
Non-target lesions	None	Stable or improved	Stable or improved	Unequivocal progressive disease*
New lesion(s)†	None	None	None	Present
Corticosteroids	None	Stable or decreased	Stable or decreased	Not applicable‡
Clinical status	Stable or improved	Stable or improved	Stable or improved	Worse*
Requirement for response	All	All	All	Any‡

\*Progression occurs when this criterion is met.

†A new lesion is one that does not present on prior scans and is visible in a minimum of two projections. If a new lesion is equivocal, for example because of its small size, continued therapy can be considered, and follow-up assessment will clarify if the new lesion is new disease. If repeat scans confirm there is definitely a new lesion, progression should be declared using the date of the initial scan showing the new lesion. For immunotherapy-based approaches, new lesions alone do not define progression.

‡Increase in corticosteroids alone will not be taken into account in determining progression in the absence of persistent clinical deterioration.

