## STUDY SCHEMA

## STUDY CALENDAR

Procedure	Screening 	Radiosurgery Delivery	Surgical Resection	Post-Surgical Resection Visit	Follow-up  (until 18-months from post-surgical resection visit) (18 months)
Study Day/Visit Day	Day – 30 to Enrollment	Day 1	Day 2 (+8 days)	1-month ±7 days from radiosurgery	Every 3 months ±14 days
Informed Consent	X				
AE Reporting	X	X	X	X	
Concomitant Medications	X	X	X	X	X
SRS		X		X	
Physical Exam 	X			X	X
Medical History	X				
ECOG Performance Status	X			X	X
Pregnancy Test (Serum or Urine) 	X				
Neurocognitive Testing 	X				
QOL Questionnaire 	X			X	X
MRI (Brain) 	X			X	X

1. All screening procedures must occur within 30 days prior to enrollment. Treatment must start within 14 days of enrollment.
2. If a subject has disease progression/relapse or subject withdrawal, then they will be followed as per follow-up requirements.
3. Including height and weight on screening. Temperature, HR, RR, BP and O2 sats or as per institutional standards at all timepoints.
4. For women of childbearing potential, a negative pregnancy test (serum or urine) must be obtained within 30 days prior to the first study intervention.
5. Neurocognitive testing: Multilingual Aphasia Examination Controlled Oral Word Associated Test (COWAT), Trail Making Test, Parts A and B (TMT), and Hopkins Verbal Learning Test-Revised (HVLT-R).
6. QOL Questionnaire: MDASI-BT, EQ-5D-5L.
7. MRI (brain) w/ contrast. Radiographic assessments will be completed as per RANO criteria (see Appendix 3).

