## **2.4 Secondary Endpoint(s)**

1. CNS progression-free survival and overall survival will be evaluated at six, 12, and 18 months following surgical resection.
2. Rates of leptomeningeal carcinomatosis using preoperative GK-SRS will be documented and compared to historically cited rates for postoperative GK-SRS.
3. Incidence of radiation necrosis will be measured by post-treatment MRI.
4. Quality of life measures will be collected and will be compared to historically cited data.

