#### Inclusion Criteria

1. Voluntary written consent must be given before performance of any study-related procedure that is not part of standard medical care, with the understanding that consent may be withdrawn by the subject at any time without prejudice to future medical care.
2. English speaking.
3. Female or male subject's  $\geq$  18 years old at the time of informed consent.
4. Radiographically confirmed solid tumor brain metastases.
5. Criteria for surgical resection of at least one metastasis per neurosurgeon discretion.
6. Stereotactic radiosurgery candidate per radiation oncologist discretion.
7. A diagnostic MRI brain or CT head demonstrating the presence of one to four solid tumor brain metastases and lesion to be resected no more than 5 cm in any direction, performed within 30 days prior to stereotactic radiosurgery.
8. For known and unknown primary, ds-GPA estimated median survival no less than six months.
9. Surgical resection able to be performed within one to 10 days after radiosurgery.
10. Patients currently on cytotoxic chemotherapy or immunotherapy are eligible, not including anti-VEGF therapy.
11. Female subjects who:
  - a. Are postmenopausal for at least one year before the screening visit, OR
  - b. Are surgically sterile, OR

If they are of childbearing potential:

- i. Agree to practice one highly effective method and one additional effective (barrier) method of contraception, at the same time, from the time of signing the informed consent through four months after the last study Intervention (female and male condoms should not be used together), OR
- ii. Agree to practice true abstinence, when this is in line with the preferred and usual lifestyle of the subject. (Periodic abstinence [e.g., calendar, ovulation, symptothermal, post-ovulation methods] withdrawal, spermicides only, and lactational amenorrhea are not acceptable methods of contraception.)

CRC Initials: \_\_\_\_\_

Date: \_\_\_\_\_

Investigator/Enrolling Physician Initials: \_\_\_\_\_

Date: \_\_\_\_\_

12. Male subjects, even if surgically sterilized (i.e., status post-vasectomy), who:

- Agree to practice effective barrier contraception during the entire study treatment period from the time of signing the informed consent through and through four months after the last study intervention (female and male condoms should not be used together), OR

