#### 5.1.1 Stereotactic Radiosurgery

SRS will be delivered utilizing Gamma Knife®. Target volume and isocenter determination will be based on a brain MRI with the patient's head in the stereotactic frame or face mask. SRS will be delivered to each lesion that has not previously undergone treatment. Due to the volumetric summation constraint for the remaining metastases, no single, non-resected lesion greater than 5 cm will be allowed in the study.

If any two lesions are within 0.8 to 2 cm of each other, the intervening midplane dose will not exceed 15 Gy. This may require treating each respective target with a lesser dose than dictated by the above dosing criteria to minimize toxicity. The dose to the critical structures, including optic pathway, brainstem, cochlea, and medulla, must meet constraints as determined by the radiation oncologist. If the above constraints cannot be met utilizing the prescribed radiosurgery dose, then the highest dose to the target volume will be used such that constraints can be met. This will be considered a minor deviation.

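### Appendix 3 sets no absolute minimum for growth, so where a small unresected lesion is the only target lesion, a 1–2 mm reading change counts as a CNS-PFS event

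*Combined protocol and SAP*

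**What the plan says.** **The rule.** In Appendix 3, target-lesion progression is "≥20% increase in sum longest distance relative to nadir", and stable disease is bounded by its mirror image, "<20% increase in sum longest distance relative to nadir". The asterisk on the progression cell reads "Progression occurs when this criterion is met". All three footnote marks in the table have their text. None adds a millimetre minimum, a smallest measurable lesion or a confirmatory scan for growth. Repeat scanning appears only for equivocal new lesions: "If repeat scans confirm there is definitely a new lesion, progression should be declared using the date of the initial scan showing the new lesion". The other routes to progression are unequivocal non-target progression, a new lesion, or worse clinical status. Any one is enough.

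**Where it applies.** Study Calendar footnote 7 says "Radiographic assessments will be completed as per RANO criteria (see Appendix 3"). Section 2.4 says "CNS progression-free survival and overall survival will be evaluated at six, 12, and 18 months following surgical resection", and section 7.2 plans Kaplan-Meier estimates. Neither section defines the event.

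**Which lesions are exposed.** Inclusion criterion 7 allows one to four metastases. Under section 3.2 all are irradiated and only resectable ones are removed, so up to three can remain. The lowest size band in section 5.1 is 2 cm or less, with no lower limit.

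**Baseline.** The eligibility scan (MRI or CT) is "performed within 30 days prior to stereotactic radiosurgery". Section 5.1.1 says "Target volume and isocenter determination will be based on a brain MRI", but the calendar marks no MRI in the Radiosurgery Delivery column. No passage says which scan is the baseline.

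**The concern.** A purely relative threshold asks for very little absolute change when the sum is small. Using the lowest earlier reading as comparator adds to this, because the minimum of several noisy readings tends to lie below the true size. A treated lesion that has not changed can therefore cross 20% through measurement error alone, and nothing printed for target lesions would stop the call.

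The effect runs one way: false events lower CNS-PFS. With 10 completed patients, one false event moves a landmark estimate by about 1/10, or 10 percentage points. Section 3.2 intends to set CNS-PFS beside historically reported rates, so a shift of that size could change how the result reads.

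**Working it through.** The plan derives no figure from this threshold, so there is none to reproduce. The documents also give no reading error. SDs of 0.5, 1.0 and 1.5 mm are assumptions, as are normal errors independent between scans.

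**1. Trigger in millimetres** when the lesion is alone in the sum (0.2 × diameter): 5 mm → 1.0; 8 mm → 1.6; 10 mm → 2.0; 15 mm → 3.0; 20 mm → 4.0. From a sum of 25 mm upwards, 20% is already at least 5 mm.

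**2. One comparison.** For a stable lesion of diameter d and reading SD s, the second reading is at least 1.2 times the first with probability

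P = 1 − Φ(0.2d / (s√(1 + 1.2²))), where √2.44 = 1.562.

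For d = 10 mm:
- s = 0.5: 2/0.781 = 2.56, P = 0.5%
- s = 1.0: 2/1.562 = 1.28, P = 10%
- s = 1.5: 2/2.343 = 0.854, P = 20%

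**3. Which scans precede each landmark.** The calendar places scans nominally at months 1, 4, 7, 10, 13, 16 and 19 after radiosurgery. Surgery is 1 to 10 days after radiosurgery, so the six-month landmark falls shortly after month 6. Only the month-1 and month-4 scans come before it. The 18-month landmark takes in scans to month 16.

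**4. Repeated comparison with the running minimum.** Simulation with 200,000 runs: constant true size, a baseline reading plus the scans above, progression at the first reading of at least 1.2 times the lowest earlier sum.

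| Target lesions | SD (mm) | By month 4 | By month 16 |
|---|---|---|---|
| One, 10 mm | 0.5 | 1.5% | 8% |
| One, 10 mm | 1.0 | 24% | 70% |
| One, 10 mm | 1.5 | 42% | 90% |

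Other cases by month 16:
- Two 10 mm lesions in the sum, SD 1.0: 37%. Three: 17 to 18%. At SD 0.5, two or three give under 1%.
- One 15 mm lesion, SD 1.0: 31%.
- One 20 mm lesion: about 0%, 8% and 43% at SD 0.5, 1.0 and 1.5.
- One 5 mm lesion: 70% at SD 0.5 and 96% at SD 1.0.

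**5. Expected false events at six months.** If 4 of 10 patients had a single 10 mm target lesion (assumption): 4 × 0.015 = 0.06, 4 × 0.24 = 0.96 or 4 × 0.42 = 1.68 for the three SDs.

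**6. Effect of also requiring 5 mm,** one 10 mm lesion: by month 16, 70% falls to 0.4% at SD 1.0 and 90% falls to 13% at SD 1.5. By month 19 the rates are about 0.5% and 16%.

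**7. Price of requiring 5 mm.** With volume doubling time T, diameter grows by a factor k in 3T·log₂k days. For T = 180 days (assumption):
- 20% growth: 540 × 0.263 = day 142
- 10 mm lesion plus 5 mm (k = 1.5): 540 × 0.585 = day 316, which is 174 days later, about two scan intervals
- 5 mm lesion plus 5 mm (k = 2): day 540, which is 398 days later, over four scan intervals

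At T = 90 days, a 5 mm lesion moves from day 71 to day 270.

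**8. Baseline timing.** Diameter growth over 30 days is 2^(30/(3T)) − 1: 26%, 12% or 8% for T = 30, 60 or 90 days (assumptions). This counts toward the 20% only if the earlier scan is used as baseline and no later reading is lower.

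**The case against.** **The appendix is a summary of a cited source.** It does not define target lesion, measurability or baseline, so fuller criteria may be intended. Whether that source has an absolute minimum cannot be checked from the documents. What stands is that the plan prints no minimum, and the printed rule is the one a reader of scans would follow.

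**Not every small lesion need be a target lesion.** A reader might infer that a 20% rise is the plan's only progression rule. It is not: a lesion classed as non-target needs unequivocal progression, which guards against reading noise. That protection is real, but no rule says which lesions are targets.

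**The single 10 mm lesion is an unfavourable case.** The rule applies to the sum, so further lesions dilute the error, and the result runs from 8% to 90% by month 16 on the assumed SD alone. This is correct. The documents do not establish that the effect is large in this trial.

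**A millimetre minimum exchanges one error for another.** Also correct: it would miss or delay true growth in small lesions and push CNS-PFS upward, and the documents contain no basis for 5 mm in particular. A reader might take the delay to be one scan; step 7 shows that it can be two to over four.

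**The endpoint is secondary and descriptive, in a feasibility pilot.** That limits the weight of the point but does not close the gap in the definition.

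**Conclusion.** The point holds in limited form. As printed, Appendix 3 can turn a 1–2 mm reading change into a CNS-PFS event when a small, stable, unresected lesion is the only target lesion. For one 10 mm lesion the false-call probability is about 1.5% to 42% before the six-month landmark and 8% to 90% by month 16, over assumed SDs of 0.5 to 1.5 mm. It is small for lesions of 20 mm or more at SD 1.0 mm or less. It is nil for a patient whose only metastasis is fully resected. The link to CNS-PFS runs through calendar footnote 7, because the endpoint has no event definition of its own.

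Three stronger readings are not supported:
- The month-7 scan might be counted toward the six-month landmark, but on the nominal calendar it falls after it.
- The screening scan might be taken as a wrongly chosen baseline. The documents leave the baseline undefined.
- A false call might be thought to set off salvage therapy. Section 5.1.2 links salvage to progression of residual disease, but nothing says that the Appendix 3 threshold alone decides it.

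**What to change.** Change the CNS-PFS endpoint definition only, and say that it is not a treatment trigger.

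- **Appendix 3 and section 7.2:** define size progression of target lesions as a rise of at least 20% over nadir together with an absolute increase in at least one lesion. 5 mm is an example; the sponsor should choose and justify the figure.
- **Appendix 3:** state the smallest measurable lesion and how target lesions are selected, and assess lesions below that size under the existing non-target row.
- **Baseline:** name the SRS planning MRI, already required by section 5.1.1, as the baseline scan and mark it in the Radiosurgery Delivery column of the calendar.

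This is wording only, needs no extra scan, and is best settled before images are read. State the downside in the plan: true growth of a small lesion may be called two or more scans later, and over four for a slow-growing 5 mm lesion, unless the non-target rule catches it first.
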